## 4.10 Efficacy Evaluation

For all efficacy analyses the Full Analysis Set (FAS) will be used unless otherwise specified. Efficacy will be assessed based on spirometry, subject-reported outcomes (SGRQ, BDI/TDI) and rescue medication usage. A summary of the efficacy variables used in the statistical analyses is given in Table 6.

Efficacy Va	riable	Analysis Set	Objective	Visit Day	Data Type	Analysis Model
Spirometry	CBL Trough FEV 1	FAS	Primary	Day 85	Continuous	MMRM (MAR)
	CBL Trough FEV 1	РР	Supportive	Day 85	Continuous	MMRM (MAR)

**Table 6: Summary of Efficacy Endpoints** 

	CBL Trough FEV 1	FAS	Sensitivity	Day 85	Continuous	ANCOVA (LOCF)
	CBL Trough FEV 1	FAS	Sensitivity	Day 85	Continuous	MMRM (Tipping Point MI)
	CBL Trough FEV 1	FAS	Sensitivity	Day 85	Continuous	MMRM (Subgroup Analyses)
	CBL Trough FEV 1	FAS	Secondary	Day 29, 57	Continuous	MMRM
	CBL Trough FVC	FAS	Secondary	Day 29, 57 and 85	Continuous	MMRM
	CBL Peak FEV 1 0-2h	FAS	Secondary	Day 1	Continuous	ANCOVA
	CBL Peak FEV 1 0-2h	FAS	Secondary	Day 85	Continuous	ANCOVA
	CBL Weighted Mean FEV 1 0-2h	FAS	Secondary	Day 1, 85	Continuous	ANCOVA
SGRQ	SGRQ responder	FAS	Secondary	Day 85	Binary	Logistic Regression
	CBL SGRQ total score	FAS	Secondary	Day 85	Continuous	ANCOVA
	CBL SGRQ component scores (3)	FAS	Other	Day 85	Continuous	ANCOVA
BDI/TDI	TDI focal score	FAS	Secondary	Day 85	Continuous	MMRM
	TDI focal score	FAS	Secondary	Day 29, 57	Continuous	MMRM
	TDI component scores (3)	FAS	Other	Day 29, 57, 85	Continuous	MMRM

	TDI responder	FAS	Secondary	Day 29, 57, 85	Binary	MMRM logistic model
Rescue Medication Usage	Average Count of Salbutamol Puffs Per Day	FAS	Secondary	Month 1,2,3 and Overall (Day1-85)	Continuous	MMRM
	Percentage of monthly salbutamol rescue free 24-hour periods	FAS	Secondary	Month 1,2,3 and Overall (Day1-85)	Continuous	MMRM

## 4.10.1 Analysis and Data Conventions

#### 4.10.1.1 Multicenter Studies

This multicenter study utilizes a central randomization stratified by concomitant LABA use and reversibility to ipratropium. All centers will be in China. Center will not be included as a fixed effect covariate in the statistical analyses due to the small numbers at each site.

4.10.1.2 Adjustments for Covariates

As the randomization is stratified by concomitant LABA use (Yes, No) and reversibility to ipratropium (Yes, No), these will be included as covariates in all analysis models.

Other factors to be included in the statistical models for efficacy as fixed-effect class terms are smoking status (current smoker, ex-smoker); age category (<65,  $\geq 65$ ); Sex (Male, Female).

A covariate for baseline  $FEV_1$  will be included in all  $FEV_1$  analysis models. Full details of the covariates used in each statistical model are outlined by endpoint in Sections 4.10.2 and 4.10.3.

#### 4.10.1.3 Handling Missing Data

Missing or unavailable data will be queried by Data Management. Data that remains missing will be identified in summaries and analyses of that data item.

For any subject who withdraws prematurely from study treatment, all available data up to the time of discontinuation of study treatment will be considered for inclusion in the analyses. An Early Termination visit will occur as soon as possible after their last dose of study drug.

The following graphical representations are examples of plots that may be used to explore the data and help to explain any dropout patterns. The actual plots used will be dependent on the final dropout rate/pattern for the study:

- Kaplan-Meier plots of time to discontinuation of study treatment split by treatment group.
- Kaplan-Meier plots of time to discontinuation of study treatment split by treatment group and reason for discontinuation (e.g. Lack of Efficacy, Adverse Events).
- Kaplan-Meier plots of time to discontinuation of study treatment split by treatment group and relationship to public health emergency (related, not related).

## Imputing Missing Data

Missing data will only be imputed in the sensitivity analyses for the primary analysis of the primary endpoint (change from baseline trough FEV1 at Day 85). Otherwise, missing data will not be imputed.

Missing data in the primary efficacy analysis is not directly imputed and is assumed to be missing at random (MAR). In sensitivity analyses the following approaches will be used for imputing missing data:

Non-monotone missing data (e.g. subjects have missing values for intermediate visits, but have available data at subsequent visits) will be assumed to be MAR. For monotone missing data the following missing data imputation methods will be used to assess the robustness of the conclusions to the MAR assumption since it may be biased and attribute treatment benefit to withdrawals even though they are no longer taking the study treatment:

- Last-Observation-Carried Forward (LOCF) single imputation method
- Two-dimensional Tipping-point multiple imputation method

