## LOCF Analysis

Missing trough  $FEV_1$  data on Day 85 will be imputed using LOCF single imputation method. Changes from baseline on Day 85 that include the LOCF imputed values will then be analyzed using an Analysis of Covariance (ANCOVA) model.

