## 4.12 Determination of Sample Size

The objective of this study is to confirm the efficacy of 12 weeks treatment with revefenacin 175 mcg compared with placebo administered once-daily in subjects with moderate to very severe COPD. The primary endpoint is change from baseline trough  $FEV_1$  at Day 85. The comparison of interest for the primary analysis is revefenacin 175 mcg versus placebo.

For each test on each efficacy endpoint, the null hypothesis is that there is no difference between the treatment groups.

H0: 
$$\mu_{rev} - \mu_{pbo} = 0$$

The alternative hypothesis is that there is a difference.

 $H_1: \ \mu_{rev} - \mu_{pbo} \neq 0$ 

The estimate for the difference in mean change from baseline trough  $FEV_1$  at Day 85 and the common standard deviation are based on the sample size assumptions for the revefenacin US pivotal studies (0126 and 0127) in a Western population and the GLOW7 study - a similarly designed study in a predominantly Chinese population (Wang et al., 2015).

A sample size of 256 evaluable subjects (128:128; a 1:1 ratio of revefenacin to placebo) is required to provide at least 90% power to detect a difference between revefenacin and placebo of 100 mL in the analysis of the change from baseline trough FEV1 at Day 85 assuming a standard deviation of 245 mL and a two-sided 5% significance level.

To allow for a 20% dropout rate, approximately 320 subjects in total will be randomized. In the event of a public health emergency such as COVID-19, the Sponsor may consider increasing enrollment to overcome any additional loss of information for the primary endpoint due to the inability of subjects to attend for scheduled clinic visits. The maximum number of subjects to be randomized under such circumstances will be limited to 428 (an additional 20% increase in enrollment).

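### LOCF is offered as a check on crediting benefit to subjects who have stopped treatment, but it carries a largely on-treatment value to Day 85 and gives little or no test of that concern

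*SAP*

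**What the plan says.** The primary analysis is an MMRM on the Full Analysis Set, using data from before treatment discontinuation and assuming MAR (SAP 4.10.2.1). Under Imputing Missing Data, SAP 4.10.1.3 explains why that assumption needs testing for monotone missing data: "since it may be biased and attribute treatment benefit to withdrawals even though they are no longer taking the study treatment". It lists two methods for the purpose: "Last-Observation-Carried Forward (LOCF) single imputation method" and "Two-dimensional Tipping-point multiple imputation method".

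For the first, the SAP states that missing trough FEV1 "data on Day 85 will be imputed using LOCF single imputation method", followed by an ANCOVA of the Day 85 change (SAP 4.10.1.3 and 4.10.2.2). Protocol 7.3.4 names the same analysis.

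For the second, shifts are subtracted from imputed revefenacin values and added to imputed placebo values. The result is judged by how plausible the tipping shift is, and Appendix 6.3 displays p-values in a two-dimensional grid (Table 7).

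An Early Termination visit is to follow the last dose as soon as possible, with no outer limit given. Its spirometry is mapped to an analysis visit by Table 4 (SAP 4.3.3).

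**The concern.** The stated threat is that subjects who have stopped the drug are credited with its benefit at Day 85. LOCF gives such a subject the last recorded change as the Day 85 value. If that value was recorded on treatment, the benefit is credited again by another route. The single imputation also treats filled values as if they had been observed.

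At stake is how the supportive evidence will be read. If LOCF and the MMRM agree in the study report, the SAP's wording invites the conclusion that the concern has been examined and dismissed. LOCF would tend to agree whether or not benefit is lost after stopping.

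**Working it through.** **Inputs (SAP 4.12).** Difference and power: "at least 90% power to detect a difference between revefenacin and placebo of 100 mL". Variability and test: "assuming a standard deviation of 245 mL and a two-sided 5% significance level". Evaluable subjects: 128 per arm. Withdrawal: "To allow for a 20% dropout rate, approximately 320 subjects in total will be randomized", that is, 160 per arm.

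**The plan's own figure.** n per arm = 2 × (245/100)² × (1.960 + 1.282)² = 126.1, rounded up to 127 (254 in total). With the noncentral t distribution, power is 0.8998 at 127 per arm and 0.902 at 128, so 128 per arm is right. 256 / 0.80 = 320. The sample size reproduces and is not in dispute.

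**Assumptions for the check (the documents give no figures).** The on-drug effect is a constant 100 mL, a share *d* withdraws in each arm, and the benefit is fully lost after stopping. The carried value retains a share *r* of the benefit.

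- Day 85 difference with the benefit removed = 100 × (1 − *d*)
- Day 85 difference under LOCF = 100 × (1 − *d*) + 100 × *d* × *r*

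| Withdrawal *d* | Benefit removed | LOCF, *r* = 1 | *r* = 0.75 | *r* = 0.5 | *r* = 0.25 | *r* = 0 |
|---|---|---|---|---|---|---|
| 10% | 90 mL | 100 | 97.5 | 95 | 92.5 | 90 |
| 20% | 80 mL | 100 | 95 | 90 | 85 | 80 |
| 30% | 70 mL | 100 | 92.5 | 85 | 77.5 | 70 |

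LOCF reaches the benefit-removed figure only when the carried value already holds none of the benefit.

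**Simulation.** 160 per arm, three visits, SD 245 mL, assumed between-visit correlation 0.7, Day 29 value carried forward, 3,000 replicates. MAR was represented by regression imputation from Day 29 within arm, not by the full MMRM.

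- Random 20% withdrawal: LOCF 99.8 mL, MAR 99.8 mL, benefit removed 79.7 mL.
- Withdrawal driven by poor Day 29 values (about 27% placebo, 21% revefenacin): LOCF 101.3 mL, MAR 99.6 mL, benefit removed 79.0 mL.

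In neither case did LOCF move towards the benefit-removed figure.

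**Power, for scale only.** Withdrawals are kept in these analyses, so the relevant number is 160 per arm. SE = 245 × √(2/160) = 27.4 mL.

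- At 100 mL: 100/27.4 − 1.96 = 1.69, power 95.5%.
- At 80 mL: 80/27.4 − 1.96 = 0.96, power 83%.

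Both figures are before any variance added by multiple imputation.

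**The case against.** **The threat is already tested.** The tipping-point analysis penalises revefenacin withdrawals directly. Its cell at −100 mL on revefenacin and 0 on placebo is close to the scenario above: 100 − 0.20 × 100 = 80 mL. An estimate and confidence interval are calculated at each shift. This stands, so a reader who infers that the plan has no protection against the concern goes too far. What remains is that Table 7 shows only p-values and identifies no cell as the benefit-stops case. Separately, the text of Appendix 6.3 gives the shifts the opposite signs (+50 mL revefenacin, −50 mL placebo) from SAP 4.10.1.3 and Table 7. These must be reconciled before the tipping point carries the weight.

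**The carried value may be partly off-treatment.** A reader might infer that LOCF cannot show any loss, or that it is the same as MAR. The documents do not support either reading. Early Termination spirometry is taken after the last dose and may follow an exacerbation that led to stopping. It can be mapped to a visit and carried, and from Day 72 onward it counts as the Day 85 value itself. LOCF also uses the subject's own last value, not a model trajectory. But the visit is meant to be prompt, SAP 4.10.1.3 leaves it unclear whether values after discontinuation count, and the SAP does not rely on this route.

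**Consequence is small.** LOCF is labelled a sensitivity analysis in Table 6, the protocol pre-specifies it, and no decision rule depends on it. This stands.

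**Power should not be overstated.** Pairing 80 mL with the 128-per-arm standard error, 245 × √(2/128) = 30.6 mL, gives 74%. That counts dropout twice: the 128 already excludes withdrawals, and the 80 mL arises only when they are kept in.

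**Conclusion.** The point holds as a mismatch between LOCF's stated purpose and what it does. It gives little or no test of benefit credited after stopping, and its agreement with the MMRM should not be reported as evidence on that question.

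Under the planned 100 mL effect, 20% withdrawal and full loss after stopping, LOCF misses up to 20 mL: it returns 100 mL against 80 mL. The gap would be up to 10 mL at 10% withdrawal and 30 mL at 30%, and it shrinks as the carried value retains less benefit. Constant effect, complete loss, equal withdrawal in the two arms and the retained share are all assumptions.

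The finding does not touch the primary analysis or the sample size, and it does not require LOCF to be dropped. It is a minor weakness that is cheap to mend.

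**What to change.** 1. Keep LOCF, because the protocol names it, but label it supplementary. Reword the passage in SAP 4.10.1.3 so that LOCF is not presented as a test of benefit credited after withdrawal.
2. Add one reference-based multiple imputation: monotone-missing revefenacin values after discontinuation are imputed from the placebo distribution, and values missing while a subject is still on drug stay under MAR. Report the Day 85 difference with its 95% CI. The imputation, MMRM and pooling steps described in Appendix 6.3 provide the framework. The SAS listings are not in the text available, so how much code can be reused could not be checked.

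The cost is one more imputation run and a supportive estimate that may be slightly less favourable. Protocol section 7 lets the SAP modify planned analyses and asks for an amendment only for major changes to the primary endpoint or its analysis, which this is not. If the database is already locked, SAP 4.13 places the change in the clinical study report.

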## LOCF Analysis

Missing trough  $FEV_1$  data on Day 85 will be imputed using LOCF single imputation method. Changes from baseline on Day 85 that include the LOCF imputed values will then be analyzed using an Analysis of Covariance (ANCOVA) model.

## **Tipping-Point Analysis**

A Tipping-point analysis will be performed. Monotone missing data at all missing scheduled visits will have the value of a shift parameter (e.g. 50 mL) subtracted from the revefenacin treatment arm (worsening results) and added to the placebo arm (improving results) for change from baseline trough FEV1. The imputed datasets will then be analyzed using the MMRM primary analysis method and an estimate for the difference between the two treatments and associated 95% CI and p-value calculated. This method will be applied iteratively where at each iteration, monotone missing values are adjusted with a larger shift parameter than at the previous iteration (e.g. by 50 mL from 0 mL to -500 mL on revefenacin and 0 mL to +500 mL on placebo). This process continues until the difference between revefenacin and placebo is no longer statistically significant. This point is called the tipping point. The plausibility of the value of the shift parameters needed to change a statistically significant result (p<=0.05) to not significant (p>0.05) will be clinically assessed.

Details of tipping-point multiple imputation method are described can be found in Appendix.

4.10.1.4 Multiple Comparisons

No adjustment for multiple comparisons is required.

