## 3.2 Endpoints

#### **3.2.1 Efficacy Variables**

In the following section, the efficacy endpoints have been defined more precisely than they were in the protocol. Therefore, definitions may differ slightly from the protocol. For example, "Change from baseline" is included in the primary endpoint definition.

- Primary endpoint
  - Change from baseline (CBL) Trough FEV1 on Day 85
- Secondary endpoint

- CBL to Peak FEV1 (0-2h) on Day 1
- Number (%) of St. George's Respiratory Questionnaire (SGRQ) responders (total score ≥4 units) on Day 85
- Transition Dyspnea Index (TDI) focal score on Day 85
- Average count of salbutamol puffs per day (Days 1-85)
- Percentage of salbutamol rescue free 24h periods (Days 1-85)
- CBL Trough FEV1 on Days 29 and 57
- TDI focal score on Days 29 and 57
- CBL in Weighted Mean FEV1 (0-2h) on Days 1 and 85
- CBL to Peak FEV1 (0-2h) on Day 85
- CBL Trough FVC on Days 29, 57 and 85
- CBL SGRQ total score on Day 85
- Number (%) of TDI responders (focal score  $\geq 1$ ) on Days 29, 57 and 85

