## 4.3.4 General Reporting Conventions

Continuous data will be summarized in terms of the mean, standard deviation (SD), median, minimum, maximum and number of observations (n), unless otherwise stated. The minimum and maximum will be reported to the same number of decimal places as the raw data recorded in the database. The mean and median will be reported to one more decimal place than the raw data recorded in the database. The standard deviation will be reported to two more decimal places than the raw data recorded in the database. In general, the maximum number of decimal places reported shall be four for any summary statistic.

Categorical data will be summarized in terms of the number of subjects providing data at the relevant time point (n), and percentages. Any planned collapsing of categories will be detailed in the SAP text and the data displays. Percentages will be presented to one decimal place. Percentages will not be presented for zero counts. Percentages will be calculated using the number of subjects in the analysis set (N) as the denominator.

Descriptive statistics for the 12-week study period will be presented by treatment group and visit, as applicable.

All statistical tests will be two-sided and will be conducted at the 5% significance level, unless otherwise specified.

P-values greater than or equal to 0.0001, in general, will be presented to four decimal places. P-values less than 0.0001 will be presented as "<0.0001".

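### Every secondary endpoint falls under two-sided 5% testing with no gate, order or nominal label, so at least 19 secondary comparisons can be called significant without error control.

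*SAP*

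**What the plan says.** Three statements in the SAP act together.

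- Section 4.10.1.4, in full: "No adjustment for multiple comparisons is required".
- Section 4.3.4: "All statistical tests will be two-sided and will be conducted at the 5% significance level, unless otherwise specified".
- Section 4.12: "For each test on each efficacy endpoint, the null hypothesis is that there is no difference between the treatment groups".

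Section 3.2.1 names one primary endpoint, change from baseline in trough FEV1 on Day 85, and twelve secondary efficacy bullets. Several bullets cover more than one visit, for example "TDI focal score on Days 29 and 57" and "CBL Trough FVC on Days 29, 57 and 85". Section 4.10.3 asks for two-sided p-values for the continuous secondary endpoints. For the SGRQ and TDI responder endpoints it asks for an odds ratio with a 95% confidence interval.

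Neither document makes secondary testing depend on the primary result, splits alpha, names key secondary endpoints, or says that secondary p-values are nominal or descriptive.

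**The concern.** With one primary endpoint, one comparison and no interim analysis, the primary test needs no adjustment. The gap is in what follows it. A null hypothesis is set for each efficacy endpoint and each is tested at 5%, so a report that follows the SAP to the letter may call any secondary result with p<0.05 statistically significant. No rule separates one such result among 19 from a supported finding.

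This matters most for the patient-reported outcomes and rescue use. Patient-reported outcomes form a stated secondary objective, and the documents cite no earlier revefenacin effect on them or on rescue use. The sponsor does use the distinction elsewhere: Protocol 2.2 calls an earlier pooled result in the LABA subgroup only nominally significant. This study's own secondary p-values carry no such label.

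**Working it through.** **The plan's own figure.** The only error and power figures given are for the primary endpoint. With a difference of 100 mL, SD 245 mL, two-sided 5% and 90% power, n per arm = 2 × (1.960 + 1.282)² × 245² / 100² = 126.1, so 127. The plan's 128 per arm gives 90.2% power by t-test, and 256 / 0.80 = 320 randomized. The sample size reproduces. No error rate is stated for the secondary endpoints.

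**Count of secondary comparisons (SAP 3.2.1).**

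| Endpoint | Comparisons |
|---|---|
| Peak FEV1, Day 1 | 1 |
| SGRQ responders, Day 85 | 1 |
| TDI focal score, Day 85 | 1 |
| Salbutamol puffs per day | 1 |
| Rescue-free 24h periods | 1 |
| Trough FEV1, Days 29 and 57 | 2 |
| TDI focal score, Days 29 and 57 | 2 |
| Weighted mean FEV1, Days 1 and 85 | 2 |
| Peak FEV1, Day 85 | 1 |
| Trough FVC, Days 29, 57 and 85 | 3 |
| SGRQ total score, Day 85 | 1 |
| TDI responders, Days 29, 57 and 85 | 3 |
| **Total** | **19** |

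By domain: 9 spirometry, 6 TDI, 2 SGRQ, 2 rescue. Nineteen is a minimum. SAP 4.10.3 also analyses 3 SGRQ components, 9 TDI component-by-visit scores and 6 monthly rescue estimates.

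**Chance of at least one p<0.05 if all 19 nulls are true.**

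Independent tests: 1 − 0.95^19 = 62.3%. In favour of revefenacin only: 1 − 0.975^19 = 38.2%.

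Equally correlated normal test statistics with correlation ρ: 1 − ∫ φ(g) [Φ((1.96 − √ρ·g)/√(1−ρ)) − Φ((−1.96 − √ρ·g)/√(1−ρ))]^19 dg. For one direction, drop the second Φ term. The documents give no correlation, so ρ is an assumption and a range is shown.

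| ρ | Either direction | Favouring revefenacin |
|---|---|---|
| 0 | 62% | 38% |
| 0.3 | 53% | 27% |
| 0.4 | 47% | 24% |
| 0.5 | 41% | 20.5% |
| 0.7 | 28% | 14% |
| 0.9 | 15% | 8% |

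A simulation (200,000 runs) with the four domains as blocks, within-domain correlation 0.5 to 0.9 and between-domain 0 to 0.3, gives about 30% to 51% in either direction.

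**If the nine spirometry nulls are false.** Ten comparisons remain: 1 − 0.95^10 = 40% if independent. The same integral with exponent 10 gives 29% at ρ = 0.5, 21% at 0.7 and 13% at 0.9.

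**The case against.** The strongest reply is that unadjusted secondary endpoints are a legitimate choice when they only support a single controlled primary test. The documents lean that way. The primary objective is to confirm efficacy, whereas the patient-reported outcome objective (Protocol 3.1.2, SAP 2.2) is only to characterize the effect. No passage promises a secondary claim. For the responder endpoints, 4 of the 19 comparisons, the specified analysis mentions no p-value; they become 5% tests only through the general wording of 4.3.4 and 4.12. All of this stands. It means that harm arises only if a report treats these p-values as proof. It also means that a nominal label would merely state what the objectives imply, and at present the SAP's testing language says otherwise.

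A reader might infer that some significant secondary result is likely by chance alone. The documents do not support that. The chance exceeds one half only if all 19 nulls are true and the common correlation is no higher than roughly 0.3. The measures overlap by design: repeated visits of one measure, FEV1 summaries from the same sessions, responder and continuous forms of one score, two endpoints from one diary. The all-null condition is also doubtful for spirometry, since Protocol 2.2 reports earlier trough FEV1 differences of 146 to 148 mL.

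A reader might also infer that the first five secondary endpoints are ranked as key, because they head the list in both documents and the synopsis describes analyses for those five. But the synopsis says its list is not exhaustive, and neither document ranks them or sets a testing order.

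**Conclusion.** The point holds as a gap in the rules for inference. It is not a flaw in the primary analysis, which keeps its 5% level. As written, the SAP permits significance statements on at least 19 secondary comparisons with no control of the familywise error. Under the global null that error lies between 15% and 62% over the correlations examined, and between 8% and 38% for false results favouring revefenacin. These figures assume that every secondary null is true and that the test statistics share one correlation. They do not apply to endpoints the drug really improves, so the practical exposure falls mainly on the dyspnea, health-status and rescue comparisons. Stating which p-values are confirmatory would be a cheap improvement and would settle what the trial can conclude.

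**What to change.** Replace the sentence in SAP 4.10.1.4 with wording such as: *The primary endpoint is the only confirmatory test, at two-sided 5%. All secondary and other p-values are nominal, and no claim of statistical significance will be made from them.* Limit the 5% testing statements in 4.3.4 and 4.12 to the primary endpoint. The 5% threshold in the tipping-point analysis can stay, because it concerns the primary endpoint.

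Cost: a few sentences of SAP text, with no change to the sample size, the models or the primary test. The downside is that no secondary endpoint can support a formal significance claim.

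If the sponsor wants such claims, it may instead specify, before unblinding, a fixed sequence that starts only if the primary test succeeds, each step at two-sided 5%, with everything outside the sequence nominal. The documents do not rank the secondary endpoints, so the order is the sponsor's choice. Endpoints after the first non-significant one would lose a formal claim.

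SAP 4.13 has version 2.0 completed before database lock and later modifications documented in the clinical study report. If lock has passed, the nominal label can be stated there.
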